## Digital Autoradiography

Digital autoradiography will be performed on the resected specimen for those patients who undergo surgery on the same day as the F-FMISO scan,. Two tissue samples will be analyzed. The samples will be cubes with approximate dimensions of 5mm x 5mm x 5mm. The first sample will be taken from an F-FMISO-avid ("hot") section of the resected tumor, and the second sample will be taken from an F-FMISO-negative ("cold") section of the resected tumor. In instances when the entire tumor is "cold" and the surgical specimen contains adequate tissue, the first sample will consist of representative tumor tissue and the second sample will consist of adjacent normal mucosa.

Tissue samples will be individually wrapped in heavy-duty Saran Wrap film and immersed into pre-chilled methylbutane (Fisher Scientific, Pittsburgh, PA) at

-80°C for 10 minutes. The frozen tissue samples will then be embedded in Optimal Cutting Temperature (OCT) compound (VWR Scientific, Rochester, NY) on dry ice and transferred to a -80°C freezer for 30 minutes. Sets of contiguous frozen 8μm-thick sections will be cut from each tissue sample using a Microm HM500 cryostat microtome (Microm, Waldorf, Germany) and collected on glass microscope slides. A minimum of three frozen tissue sections from each specimen will be placed in a film cassette against a Fujifilm BAS-MS2325 imaging plate (Fuji Photo Film Co, Tokyo, Japan). Latent images will be read out after a 24-48 hr exposure time using a Fujifilm BAS-1800II Bio-Imaging Analyzer (Fuji Photo Film Co) at 50μm pixel resolution. Digital autoradiography image intensity will be characterized by the machine readout parameter of photostimulable luminescence per square mm (PSL/mm2). Tracer uptake will be derived from region-of-interest analysis of the digital autoradiography images using dedicated software.

## 5.0 THERAPEUTIC/DIAGNOSTIC AGENTS

F-18 FDG is the only commercially available radiopharmaceutical approved by the FDA for the intended use in study patients/subjects.

F-18 labeled FMISO is prepared and tested for quality assurance in this study within the Cyclotron/Radiochemistry Core Facility at MSKCC. The radiopharmaceutical is being utilized in this protocol with authorization of the MSKCC Radioactive Drug Research Committee (RDRC). F-FMISO is prepared at an approximate specific activity of 1-2 Ci/μmole at end of bombardment time. For PET imaging of tumor uptake, 370 MBq (10.0 mCi) in 1-3 ml sterile saline will be administered IV. The maximum mass of fluoromisonidazole that will be administered is 1 microgram. The no observable effect level (NOEL) is at mass dose >1 milligram.

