## 3.2 F-FMISO PET

F-FMISO PET is a recently developed imaging modality useful in detecting and quantifying hypoxic regions within tumors. This tool has been studied both *in vitro* and *in vivo* across a wide range of human tumor types. While it is well established that polarographic needle electrode assessment of tissue oxygen tension is considered the "gold standard" for detecting and measuring degree of hypoxia, we continue to investigate new, less invasive techniques. A number of studies comparing F-FMISO PET imaging to needle electrode measurements in advanced head and neck tumors and soft tissue sarcomas have validated its use in studying hypoxia (13, 29)

Radiolabeled nitroimidazoles (including F-FMISO) have emerged as useful non-invasive markers of hypoxia. These molecules, in their native form, are lipophilic and freely diffusible across cell membranes. Once intracellular, they undergo an

enzymatic reduction reaction. In the presence of oxygen, this reaction is rapidly reversed and the molecule is free to diffuse out of the cell, obtaining transmembrane equilibrium. In a hypoxic environment, the reduced molecule covalently binds to intracellular macromolecules, effectively trapping it within the cell (20, 28).

At our institution, in a rat prostate cancer tumor model, as well as in two colorectal cancer xenograft models, F-FMISO microPET imaging has been used to detect tumor hypoxia. These results were corroborated by measuring pO2 directly using the OxyLite probe system (14). Preliminary results support the feasibility of imaging hypoxic subvolumes in some tumors, and we propose its use in studying colorectal tumors.

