## 4.2 Intervention

# F-FMISO PET scan

Dynamic PET scans will be performed on one of the GE Discovery PET/CT scanners in 2D mode. The patient will be set up in the radiotherapy treatment position with intra-venous lines for radiotracer injection and for venous blood sampling. A CT scan of a 15cm segment of the body (the field of view of the PET scanner) will be performed with the tumor at the field center. These images will be used for both attenuation correction and registration of the serial image set.

Immediately thereafter, a single 370 MBq (10 mCi) dose of F-MISO will be injected as a bolus, and the dynamic scan initiated coincident with the injection. Data will be acquired in 1-minute time intervals continuously from 0-30 minutes. The patient will then be removed from the scanner. Since no further F-FMISO will be injected in the patient, there will be no further radiation exposure from radiopharmaceutical. The 2nd PET scan (optional and performed at 90 minutes) and the 3rd PET scan (non-optional and performed between 120-240 minutes) will each consist of a 10-minute image of the tumor consisting of two consecutive 5minute time frames. A 15-cm body segment low dose CT scan will be performed at each of these two additional image sessions for attenuation correction and image registration. The radiation dose of the first CT scan will be 0.9 mCi and the dose for the 2nd (optional) and 3rd (non-optional) scans will be 0.1 mCi each, for a total exposure of 1.0-1.1 mCi for all 3 CT scans. This total dose is approximately equivalent to one half (1/2) of the radiation exposure from a single diagnostic CT scan. To further improve patient image registration, the patient will have markers placed on the skin, inferior and superior to the lesion, to facilitate accurate laser set-up for the subsequent 2nd (optional) and 3rd (nonoptional) scans.

Note that the patient will receive the radiation dose from only one F-FMISO injection and from 2-3 low-dose CT scans. For a detailed estimate of radiation absorbed doses to organs as a result of these scans, please refer to Table 1.

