This study will entail a single injection of 370 MBq (10 mCi) of F-MISO per patient. Absorbed dose estimates, derived from the University of Washington data, indicate that the urinary bladder wall is anticipated to experience the largest dose of any normal organ. The absorbed dose to the urinary bladder wall is estimated as 0.78 cGy (7.8 mSy) for the F-FMISO administration. Patients will receive additional radiation dose due to the CT component of the study. This contribution is estimated to be 1.1 cGy (1 mSv) for the three PET-CT scans and will be applicable only to the exposed pelvic region of the patient. The dose to the eye from the F-MISO administration is estimated to be 0.57 cGy (5.7 mSv). No additional eye dose will be delivered by CT scanning. The total body radiation dose from F-MISO is estimated to be 0.47 cGy (4.7 mSv). These estimates are well below the values of 3 cGy and 5 cGy permitted by the FDA to radiation sensitive or normal organs respectively, for an experimental radiopharmaceutical. The total radiation dose for this investigation is thus within the prescribed guidelines set for RDRC approval. Additionally, this study will not significantly add to the total radiation dose experienced by the patient as a consequence of their treatment for rectal cancer.

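### Section 5.0: the low end of the stated specific activity range does not fit the 1 microgram maximum mass at the fixed 10 mCi dose (molar mass assumed)

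*Combined protocol and SAP*

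**What the plan says.** Section 5.0 of the combined protocol and SAP makes four statements about the injected product.

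- Production: the tracer "is prepared at an approximate specific activity of 1-2" Ci/µmol, referenced to end of bombardment.
- Dose: "370 MBq (10.0 mCi) in 1-3 ml sterile saline will be administered IV".
- Limit: "The maximum mass of fluoromisonidazole that will be administered is 1 microgram".
- Safety margin: "The no observable effect level (NOEL) is at mass dose >1 milligram".

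The dose is a single value wherever it appears. Section 4.2 has "a single 370 MBq (10 mCi) dose of" the tracer, the dosimetry text in Section 5.0 has "This study will entail a single injection of 370 MBq (10 mCi) of" it, and Section 9.0 repeats the same activity. None of these places gives a range or a rule for reducing the activity.

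On batch control, Section 5.0 says: "F-18 labeled FMISO is prepared and tested for quality assurance in this study within the Cyclotron/Radiochemistry Core Facility at MSKCC". It states no lowest acceptable specific activity and no time from end of bombardment to injection. Section 3.2 places the tracer in the nitroimidazole class. No molar mass is given anywhere.

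**The concern.** Activity, specific activity and mass are tied together by one equation once the molar mass is known. If activity is fixed and specific activity may be as low as about 1 Ci/µmol, the mass follows, and a maximum has to cover that low end. The stated 1 µg appears to cover only the high end.

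What is at stake is a per-patient limit on an injected research agent used under RDRC authorization. Staff who follow the 10 mCi instruction with a batch at the low end of the described production range would exceed the protocol's own limit. Nothing in the text would tell them so, or what to do about it.

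**Working it through.** **Inputs from the documents (Section 5.0).** Activity A = 10.0 mCi = 0.010 Ci. Specific activity S = 1-2 Ci/µmol at end of bombardment. Stated maximum = 1 µg. No-effect level above 1 mg (1000 µg).

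**Assumed inputs, not in the documents.** Molar mass M = 189 g/mol, from the formula C6H8FN3O3 and atomic weights, with a range of 180-200. F-18 half-life = 109.8 min. Delay from end of bombardment to injection = 0-120 min.

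**Formula.** Mass (µg) = A / S × M, since g/mol equals µg/µmol.

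**Step 1: where the stated 1 µg comes out.** Setting the mass to 1 µg gives S = 0.010 × 189 = 1.89 Ci/µmol at injection (1.80-2.00 for M = 180-200). The figure is therefore reproduced only near the top of the stated range with almost no decay.

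**Step 2: the low end, without the full molar mass.** At S = 1, the amount is 0.010 / 1 = 0.010 µmol. For this to weigh 1 µg, M must be 1 / 0.010 = 100 g/mol or less. The nitroimidazole core C3H3N3O2 is 113.1 g/mol. Replacing one hydrogen by fluorine gives 113.1 − 1.0 + 19.0 = 131.1 g/mol, hence 0.010 × 131.1 = 1.31 µg. The limit is exceeded before the rest of the molecule is counted.

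**Step 3: mass at 10 mCi before decay.**

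| S (Ci/µmol) | Amount (µmol) | Mass at 189 g/mol (µg) | At 180-200 g/mol (µg) |
|---|---|---|---|
| 1 | 0.0100 | 1.89 | 1.80-2.00 |
| 1.5 | 0.00667 | 1.26 | 1.20-1.33 |
| 2 | 0.0050 | 0.95 | 0.90-1.00 |

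**Step 4: effect of decay.** S at injection = S at end of bombardment × 0.5^(t/109.8). The dose stays at 10 mCi when injected, so the mass is divided by the same factor.

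| Delay (min) | Factor | Mass from 1 Ci/µmol (µg) | Mass from 2 Ci/µmol (µg) |
|---|---|---|---|
| 0 | 1.00 | 1.89 | 0.95 |
| 60 | 0.685 | 2.76 | 1.38 |
| 120 | 0.469 | 4.03 | 2.02 |

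A 2 Ci/µmol batch passes 1 µg after 109.8 × log2(2/1.89) ≈ 9 min (0 to 17 min for M = 200 to 180).

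**Step 5: margin to the no-effect level.** Taking 1 mg as its lower bound, 1000 / 1.89 ≈ 530-fold with no delay and 1000 / 4.03 ≈ 250-fold at 120 min. At M = 200 the 120-minute mass is 2.00 / 0.469 = 4.27 µg, or about 230-fold.

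**The case against.** The strongest reply is that the two statements are of different kinds. The specific activity is an approximate description of production, and the 1 µg is a limit. A limit may be tighter than typical output, in which case it acts as a release criterion. The product is tested for quality assurance, and the release specification may sit in facility records outside these documents.

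Part of this stands. The documents do not show which statement is wrong, and they do not prove that any batch over 1 µg would be released. The reading does not rescue the text, however. With activity fixed at 10 mCi, it implies an unwritten floor of about 1.9 Ci/µmol at injection. The described production range barely reaches that, and loses it within minutes. The word approximate does not help either, since the low end misses by a factor of about 1.9.

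A second reply is that the molar mass is assumed. That is why the point is confined to the low end, where the fluorinated core alone is enough. A reader might infer more: that the three statements conflict over most of the range, or that a given share of batches or patients would exceed the limit. The documents do not support that. From the core alone, the break-even before decay is 0.010 × 131.1 = 1.31 Ci/µmol, so a conflict over most of the range depends on the assumed full molar mass. The range is itself approximate, and its width says nothing about how batches are distributed within it.

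**Conclusion.** The point holds for the low end of the range. At about 1 Ci/µmol, a 10 mCi dose carries about 1.9 µg before decay at an assumed 189 g/mol (1.8-2.0 for 180-200 g/mol), and at least 1.3 µg from the fluorinated core alone. At 2 Ci/µmol it carries about 0.95 µg. Decay before injection can only add to this, so 1 µg is roughly the best case and should not stand as the maximum. The direction of the decay effect is certain; its size rests on the assumed delay and half-life.

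Severity is low. A reader might infer a safety problem from a breached mass limit, but the documents point the other way: even about 4 µg is some 250-fold below 1 mg. The primary endpoint, the 1.2 tumor-to-blood threshold, the two-stage rule and the absorbed-dose estimates do not use the administered mass and are unaffected.

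**What to change.** Keep the 10 mCi dose. In Section 5.0, state the lowest specific activity accepted at the time of injection, and set the maximum mass to 10 mCi divided by that value, times the molar mass. The sponsor should choose the floor from actual production and delivery times:

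- **Floor of 1 Ci/µmol at injection:** maximum about 2 µg. A batch at 1 Ci/µmol at end of bombardment would then fail after any delay, and one at 2 Ci/µmol after one half-life (about 110 min).
- **Batches at 1 Ci/µmol at end of bombardment usable for 1-2 hours:** the floor at injection is about 0.68-0.47 Ci/µmol and the maximum about 3-4 µg (2.76-4.03 µg at 189 g/mol). The facility's real delay should replace the assumed one.

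Keeping 1 µg and writing in a floor of about 1.9 Ci/µmol at injection is not practicable, because it would reject nearly every batch in the described range.

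The cost is a short edit to Section 5.0. The stated limit becomes two to four times higher and may need to be notified to the RDRC. There is no change to the injected activity or sample size.

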## Radionuclide dosimetry

Biodistribution data on FMISO has been obtained for 60 patients at the University of Washington School of Medicine, and dosimetry was performed. Estimates of normal organ absorbed doses following FMISO administration were published by Graham et al. (22) and are summarized in the table on the following page.

Table 1
Radiation Absorbed Doses to Organs following F-MISO administration and CT Scans

Target Organ	Median Dose	Dose (cGy)	Total Dose (cGy)
	(mGy/MBq)	per 370 MBq	per 370 MBq (10mCi)
		(10mCi) injection	injection + CT Scans
Adrenals	0.0166	1.71	0.61

Brain	0.0086	0.32	0.32
Breasts	0.0123	0.46	0.46
Gall bladder wall	0.0148	1.65	0.55
Lower Large Intestine	0.0143	0.53	1.63
Small Intestine	0.0132	0.49	2.69
Stomach	0.0126	0.47	0.47
Upper Large Intestine	0.0140	0.52	0.52
Heart Wall	0.0185	0.68	0.68
Kidney	0.0157	0.58	1.68
Liver	0.0183	0.68	1.78
Lungs	0.0099	0.37	0.37
Muscle	0.0142	0.53	0.53
Ovaries	0.0176	0.65	1.75
Pancreas	0.0179	0.66	1.76
Red Marrow	0.0109	0.40	0.40
Bone Surface	0.0077	0.28	0.28
Skin	0.0048	0.18	1.28
Spleen	0.0163	0.60	1.70
Testes	0.0146	0.54	0.54
Thymus	0.0155	0.57	0.57
Thyroid	0.0151	0.56	0.56
Urinary Bladder Wall	0.0210	0.78	1.88
Uterus	0.0183	0.68	1.78
Eye Lens	0.0154	0.57	0.57
Total Body	0.0126	0.47	0.47

This study will entail a single injection of 370 MBq (10 mCi) of F-MISO per patient. Absorbed dose estimates, derived from the University of Washington data, indicate that the urinary bladder wall is anticipated to experience the largest dose of any normal organ. The absorbed dose to the urinary bladder wall is estimated as 0.78 cGy (7.8 mSy) for the F-FMISO administration. Patients will receive additional radiation dose due to the CT component of the study. This contribution is estimated to be 1.1 cGy (1 mSv) for the three PET-CT scans and will be applicable only to the exposed pelvic region of the patient. The dose to the eye from the F-MISO administration is estimated to be 0.57 cGy (5.7 mSv). No additional eye dose will be delivered by CT scanning. The total body radiation dose from F-MISO is estimated to be 0.47 cGy (4.7 mSv). These estimates are well below the values of 3 cGy and 5 cGy permitted by the FDA to radiation sensitive or normal organs respectively, for an experimental radiopharmaceutical. The total radiation dose for this investigation is thus within the prescribed guidelines set for RDRC approval. Additionally, this study will not significantly add to the total radiation dose experienced by the patient as a consequence of their treatment for rectal cancer.

# 6.0 CRITERIA FOR SUBJECT ELIGIBILITY

## 6.1 Subject Inclusion Criteria

- Able to provide written informed consent
- Histologically confirmed diagnosis of colorectal adenocarcinoma
- 18 years of age or older
- Karnofsky performance status  $\geq 70$

# 6.2 Subject Exclusion Criteria

• Women who are pregnant (confirmed by serum b-HCG in women of reproductive age) or breast feeding

## 7.0 RECRUITMENT PLAN

All patients meeting the eligibility requirements will be considered for enrollment regardless of sex, race, or religion. A member of the colorectal research team will screen the clinics of the investigators named on the protocol to identify potentially eligible patients. These patients will be made aware of the protocol, its specific aims and objectives, and the potential risks and benefits the patient may incur. Patients will be required to read, agree to, and sign an IRB-approved informed consent form prior to registration on this trial. Patients will be consented by their treating physician.

During the initial conversation between the investigator/research staff and the patient, the patient may be asked to provide certain health information that is necessary to the recruitment and enrollment process. The investigator/re search staff may also review portions of their medical records at MSKCC in order to further assess eligibility. They will use the information provided by the patient and/or medical record to confirm that the patient is eligible and to contact the patient regarding study enrollment. If the patient turns out to be ineligible for the research study, the research staff will destroy all information collected on the patient during the initial conversation and medical records review, except for any information that must be maintained for screening log purposes

Because they will be asked to come in to the hospital for an additional day, patients will be given a \$100 honorarium to cover gas, tolls, parking, meals and any incidental expenses associated with this additional day.

## 8.0 PRETREATMENT EVALUATION

All patients will undergo standard of care tests including an FDG PET scan.

## 9.0 TREATMENT/INTERVENTION PLAN

Within six weeks of the FDG PET scan, patients will undergo an F-FMISO PET scan. Patients will receive no treatment between the two scans. The F-FMISO scan will be conducted as follows:

- An I.V. line will be placed in each of the left and right forearms (i.e., a total of 2 I.V. lines). One line will be used exclusively for radiotracer injection and the other exclusively for blood sampling (see below).
- A scout view, followed by a low-dose CT of the tumor region will be obtained.
- The couch will automatically advance into the PET detector component of the scanner so that the tumor is in the center of the 15 cm PET field of view.
- The patient will be injected intravenously with 370 MBq (10 mCi) of F-FMISO, simultaneously with the start of PET image acquisition.
- Dynamic images consisting of five 1-minute images and five 5-minutes images (duration 30-minutes) will be acquired within one 15 cm field of view.
- Patient will be taken out of the scanner.
- Patient will undergo a 2nd (optional) PET scan at 90 minutes and a 3rd (non-optional) PET scan at 120-240 minutes post-injection. These scans will consist of a 10-minute PET acquisition and a low-dose CT.
- When blood sampling is required, up to a maximum of 3 blood samples will be obtained using the second I.V. line immediately at selected times post-injection and during the PET scan procedure. Samples will be taken with each imaging time point. Between 1 and 3 cc of blood will be removed at each time point (making the maximum volume of blood withdrawn during this study < 9 cc).

• .

- These samples will be weighed and counted in the Nuclear Medicine laboratory for the purpose of determining the blood clearance kinetics and the tumor input function.
- At the end of the entire study, the I.V. lines will be removed.
- The radiopharmacy will keep a log of all injected activity. All patient doses are permanently recorded in the Nuclear Pharmacy database. The injected F-FMISO dose, injection time and scan time are also recorded in the PET image file header, and can be accessed from the PET images themselves.
- Digital autoradiography will be performed on up to two tissue samples from patients who undergo surgery on the same day as the F-FMISO scan (see details in Section 4.2, "Intervention").
- The RSA assigned to the study will be responsible for identifying eligible patients from the colorectal service clinics. The RSA will work closely with the POAs and RSAs in the Department of Radiology to coordinate scheduling of patients' research procedures and will track patients who are on study to ensure they follow the treatment schedule outlined above.

## 10.0 EVALUATION DURING TREATMENT/INTERVENTION

There are no follow-up requirements for this study. All patients will undergo standard of care for their colorectal cancer and will be evaluated accordingly.

## 11.0 TOXICITIES/SIDE EFFECTS

The safety of various radiopharmaceuticals has been reviewed. In a 5-year prospective study (1989 to 1994) of 18 institutions in the United States, the prevalence of adverse events following radiopharmaceutical administration was 0.0023% (23). The adverse experiences reported included rash, chest discomfort, light headedness, nausea, mild anaphylaxis, diaphoresis, vomiting and headache. In a prospective study of 22 PET centers from 1994 to 1997, there were no adverse events reported during 81,801 administered doses of PET pharmaceuticals (24). In a similar study of 17 nuclear medicine departments in Europe in 1996, the prevalence of adverse events was 11 events per 100,000 radiopharmaceutical administrations (25). There were no serious or lifethreatening events, and no deaths reported in the literature.

A similar study to that proposed has been carried out at MSKCC featuring FMISO PET scanning in Head and Neck cancer patients (IRB # 04-070). No side effects, including allergic reactions and claustrophobia, have been noted (16). Study patients will also be exposed to radiation during the study, both from the CT component of the PET CT and from the F-MISO itself. At the dose levels

outlined in section 5.0, there have been no reported radiation-related side effects in the literature.

In the unlikely event of an adverse reaction, this will be documented and reported by the Principal Investigator to the Institutional SAE Manager ([name]) as well as to the RDRC.

